10.1.7. Laboratory Assessments

Laboratory assessments will be performed per the Schedule of Assessments ([Table 6](#) and [Table 7](#)). All laboratory assessments are to be performed centrally unless otherwise specified. The Investigator must review results from these laboratory assessments (performed locally and centrally) and determine the clinical significance of any results outside the reference range. This review must be documented, and laboratory values considered clinically significant during this study be recorded as an AE. On the days where a dose of IP is administered, all laboratory assessments should be performed prior to dosing unless otherwise specified. A list of analytes is presented in [Table 9](#).

10.1.8. Hepatic Function Testing

Patients presenting with elevated liver function tests should be closely monitored. Any patient with an elevation of ALT or AST $\geq 3 \times$ ULN, alkaline phosphatase $\geq 2 \times$ ULN, or total bilirubin $\geq 2 \times$ ULN should have their liver function tests repeated within 3 days. If the repeat results remain above these thresholds or higher, the Investigator should conduct additional testing and consult the Sponsor Medical Monitor. Monitoring of liver function tests should continue until results stabilize or return approximately to their level prior the initial elevation.

10.1.9. Estimated Glomerular Filtration Rate

Estimated glomerular filtration rate will be calculated by the central laboratory using the Chronic Kidney Disease Epidemiology Collaboration (CKD-EPI) formula ([Levey, 2009](#)) for patients aged ≥ 18 years. For patients aged ≤ 17 years, the “Bedside Schwartz” equation ([Schwartz, 2009](#)) will be used to calculate eGFR.

10.1.10. Urine Drug Screen

Urine drug screen for drugs of abuse will be performed locally via dipstick testing on urine and may be repeated at the Investigator’s discretion. Testing kits will be provided by the central laboratory. Urine drug screens should test for the following drugs of abuse: THC, cocaine, opiates, methamphetamine, amphetamines, phencyclidine (PCP), benzodiazepine, barbiturates, methadone, tricyclic antidepressants, ecstasy, and oxycodone.

10.1.11. Follicle-Stimulating Hormone

Menopausal status of women must be confirmed by testing for FSH levels at the Screening Visit (Visit 1). To be considered menopausal, FSH level must be ≥ 30 mIU/mL and the patient must not have had a menstrual period in ≥ 1 year. Follicle-stimulating hormone testing must only be performed in women reporting menopause.

10.1.12. Pregnancy Screen

A serum pregnancy test will be performed centrally at Screening (Visit 1) in women of childbearing potential (WOCBP). All other pregnancy tests will be performed locally using dipstick testing on urine in women of childbearing potential only. Testing kits will be provided by the study site. A positive urine pregnancy test must be confirmed by sending a serum sample to the central laboratory. Women with a confirmed positive serum pregnancy test should be withdrawn from the study. The Investigator should refer the patient for appropriate care. Details on reporting and following pregnancies are provided in ([Section 10.2.9](#)).

10.1.13. Pharmacokinetic Sampling

On Visits 5 (Week 7), 8 (Week 10), 12 (Week 27), and 14 (End of Study [EOS]/Week 34), patients will have a blood sample collected for PK at the same time as their laboratory blood samples. The time of sampling will be recorded, with the exception of Visit 8 (Week 10). Pharmacokinetic sampling on Visit 8 should occur within 6 ± 2 hours of dose. The dose preceding Visit 8 PK sampling may be taken at home in order to comply with the PK sampling window. Pharmacokinetic samples at Visits 5, 12, and 14 can occur without regards to the time of dosing, as long as dosing and PK sampling times are accurately recorded.

Table 9: Laboratory Analytes

Renal Panel (10-hour fasting^a)	Hematology	HbA1c
Sodium	Hematocrit	
Potassium	Hemoglobin	Coagulation
Chloride	MCV	PT-INR
Calcium	MCH	Appetite Hormones
Bicarbonate	MCHC	Insulin
Glucose	RDW	Circulating ghrelin ^b
Phosphorus	RBC	Leptin
BUN	WBC	Urinalysis
Creatinine	Platelets	Color
eGFR	Differential (% and absolute Count)	Appearance pH
Liver Function Panel		
ALT	Neutrophils	Specific gravity
AST	Eosinophils	Protein
Albumin	Basophils	Glucose
Alkaline phosphatase	Lymphocytes	Ketones
Direct and indirect bilirubin	Monocytes	Bilirubin
Total bilirubin	Urine tests	
Total protein	Drug screen including THC ^{c,d}	Urobilinogen
Serologies		Pregnancy test ^{e,f}
HIV	Other test	
Hepatitis B surface antigen	FSH ^g	Microscopic examination if blood, protein, or leukocyte
Hepatitis C antibody	Quantitative serum pregnancy test ^h	esterase is abnormal in urine

Abbreviations: ALT = alanine aminotransferase; AST = aspartate aminotransferase; BUN = blood urea nitrogen; eGFR = estimated glomerular filtration rate; FSH = follicle stimulating hormone; HbA1c = glycosylated hemoglobin; HIV = human immunodeficiency virus; INR = international normalized ratio; MCH = mean corpuscular hemoglobin; MCHC = mean corpuscular hemoglobin concentration; MCV = mean corpuscular volume; PT = prothrombin time; RBC = red blood cells; RDW = red cell distribution width; THC = tetrahydrocannabinol; WBC = white blood cells.

All tests to be performed centrally unless otherwise specified

^a Fasting is preferred, if possible. If obtained in a non-fasting state, will not be considered a protocol deviation.

^b Includes acylated ghrelin and des-acyl ghrelin

^c Performed locally via dipstick testing and provided by the central laboratory. Must include testing for THC, cocaine, opiates, methamphetamine, amphetamines, PCP, benzodiazepine, barbiturates, methadone, tricyclic antidepressants, ecstasy, and oxycodone

^d May be repeated at any time at the Investigator's discretion

^e To be performed in females of childbearing potential only. Testing kits to be provided by the study site

^f If positive, a confirmatory pregnancy test at the central laboratory is required

^g To be performed in postmenopausal females only

^h To be performed centrally at Screening (Visit 1) and if a local urine pregnancy test is positive.

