5.8.4.1 Visit 5 (End of Screening, Beginning of Dose Escalation Period, Week 7)

The following assessments must be performed in person during Visit 5 (Week 7). All assessments must be performed prior to dosing on Visit 5, unless specified otherwise. Prior to assessing randomization eligibility, patients/caregivers must complete the HQ-CT.

- Review of concomitant medications
- Review of AEs
- Weight and height
- Vital signs, including BP, HR, temperature, RR, and oxygen saturation
- Complete physical examination
- Completion of the HQ-CT questionnaire (pre-dose)
 - The same caregiver should be available throughout the study to complete the questionnaires with the patient
 - HQ-CT must be completed prior to randomization

- Review of HQ-CT questionnaire scores and Inclusion/Exclusion criteria for eligibility
 - The EDC system will automatically calculate mean HQ-CT score from Visit 3, Visit 4 and Visit 5 inclusively. Patients with a mean HQ-CT score ≥ 13 will be eligible for randomization. Patients not eligible for randomization because of a HQ-CT score < 13 will not have the opportunity to participate in the long-term extension study (SCOUT-016)
 - The EDC system will also automatically calculate the change in HQ-CT score from Visit 2 (beginning of the Tolerability Period) to Visit 5 (end of the Tolerability Period/Beginning of Dose Escalation Period) inclusively. Patients must have a decrease in HQ-CT score ≤ 7 to be eligible for randomization and able to proceed to the Dose Escalation Period. Further details are defined in [Section 6.4](#)
 - Laboratory values collected prior to visit 5 should be used to assess eligibility
 - Patients meeting all inclusion and exclusion criteria should proceed to randomization.
 - Completion of the C-SSRS questionnaire (predose)
- Randomization
- Completion of the ABC, ESS-CHAD, CGI-S Hyperphagia, CaGI-S Hyperphagia, and Skin Picking questionnaires
- Resting 12-lead ECG in the supine position
- Collection of laboratory samples ([Section 10.1](#))
 - Urinalysis
 - Urine dipstick pregnancy test for females of childbearing potential only to be performed locally
 - Urine drug screen for drugs of abuse including THC
 - Chemistry panels (renal and liver function panels)
 - Hematology
 - Appetite hormones (including insulin, ghrelin, and leptin) Ghrelin samples will only be collected for Phase 3 patients at sites where proper collection is feasible.
- Pharmacokinetic sample ([Section 10.1.13](#))

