 - Blood draws for PK analyses of CBD, 7-OH-CBD, and 7-COOH-CBD will be drawn at the same time as the other laboratory samples. Time of sampling will be recorded
- Food diary collection
- Drug Accountability
- Investigational product (IP) dispensing

- Dosing of IP after randomization, to be completed in clinic
- Dual-energy X-ray absorptiometry (DEXA) scan
 - To be performed at certain US sites only
 - Can be performed before or after dosing of IP, within \pm 7 days of Visit 5.

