^o The EDC system will automatically calculate mean HQ-CT score from Visit 3, Visit 4 and Visit 5 inclusively. Patients with a mean HQ-CT score ≥ 13 will be eligible for randomization. In addition, the EDC system will also automatically calculate the change in HQ-CT score from the Tolerability Period to the Screening Period. Patients must have a decrease in HQ-CT score ≤ 7 to be eligible for randomization. Further details are defined in [Section 6.4](#).

^p If the patient is the mental equivalent of 6 or younger, then the children's version of the C-SSRS should be used.

^q Randomization cannot be performed prior to evaluation and review of HQ-CT questionnaire scores for eligibility. Prior to assessing randomization eligibility, patients must complete the Visit 5 HQ-CT questionnaire ([Section 6.4.2](#)).

^r For WOCBP only. If positive, a quantitative serum pregnancy test must be sent to the central laboratory for confirmation.

^s Drugs of abuse include THC. May be repeated at the Investigator's discretion.

^t Chemistry panels include renal and liver function panels. Renal function panel includes sodium, potassium, chloride, calcium, bicarbonate, glucose, phosphorus, blood urea nitrogen, creatinine, and glomerular filtration rate. Should be obtained after a 10-hour fast if possible. Liver function panel includes ALT, AST, albumin, alkaline phosphatase, direct bilirubin, total bilirubin, indirect bilirubin, and total protein ([Table 9](#)).

^u Hematology panel includes hematocrit, hemoglobin, MCV, MCH, MCHC, RDW, RBC, WBC, platelets, and differential ([Table 9](#)).

^v Includes insulin, ghrelin, and leptin ([Table 9](#)). Ghrelin samples will only be collected for Phase 3 patients at sites where proper collection is feasible.

^w Will only be performed in patients enrolled in the Phase 3 part of the study and be optional. Biomarker assessments will not be conducted in the Phase 2 part of the study

^x Must be drawn 6 ± 2 hours after the previous IP dose. Patients may take their IP dose at home prior to presenting to the site for their visit in order to comply with the PK timing requirements.

^y Dosing should be completed at the site during Visit 2 and Visit 5. Dosing is not required to be done at the site when patients have remote or other visits ([Section 7.1](#)).

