9.4. Pharmacokinetic Endpoints

Throughout the study, plasma samples will be collected to establish the PK profile of CBD and 2 metabolites, 7-OH-CBD and 7-COOH-CBD in patients with PWS. Furthermore, an exposure-response analysis using CBD and 7-OH-CBD concentrations as well as a population PK model will be derived from the data. Details on sample collection are provided in [Section 10.1.13](#) and in the Laboratory Manual.

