10.1.14. Food Diary

A food diary will be distributed to all patients on Visits 4, 7, 11 and 14 but can be distributed at the site's or patient's convenience. This food diary will be collected as per [Table 7](#). The food diary will collect time of food consumption, type and amount of food consumed, date and time of evening and morning dose, and support the pharmacokinetic analysis.

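### As written, the protocol exempts Visit 8 from recording the PK draw time, although Visit 8 is the only PK visit with a required post-dose window

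*Protocol*

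**What the plan says.** The protocol collects one PK sample at each of Visits 5, 8, 12 and 14.

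- **Recording rule.** Section 10.1.13 states: "The time of sampling will be recorded, with the exception of Visit 8 (Week 10"). Section 5.8.5.1 repeats the sentence.
- **Visit 8 timing.** Section 10.1.13 continues: "Pharmacokinetic sampling on Visit 8 should occur within 6 ± 2 hours of dose". Table 7, footnote x, is firmer: "Must be drawn 6 ± 2 hours after the previous IP dose". The preceding dose may be taken at home so that the window can be met.
- **Visits 5, 12 and 14 timing.** Under Section 10.1.13 these samples "can occur without regards to the time of dosing, as long as dosing and PK sampling times are accurately recorded". For Visit 5, Section 5.8.4.1 adds "Time of sampling will be recorded", and also "All assessments must be performed prior to dosing on Visit 5, unless specified otherwise".
- **Dose time.** The food diary (Section 10.1.14) captures "date and time of evening and morning dose, and support the pharmacokinetic analysis". Section 5.8.5.1 has it collected before the blood draw at Visits 8, 12 and 14.
- **Use of the data.** Section 9.4 plans an exposure-response analysis on CBD and 7-OH-CBD concentrations, "as well as a population PK model will be derived from the data".

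**The concern.** A population PK model relates each concentration to the actual time since dose, which needs two clock times: the dose and the draw. At Visit 8 the protocol provides for the first and exempts the second.

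Two things follow if sites apply the text literally. The analyst has to place the sample at a nominal 6 h when it may lie anywhere from 4 to 8 h after dose, and this adds error to the individual exposure estimates that the exposure-response analysis will use. Also, nobody can confirm from protocol-required data that the mandatory window was met. Visit 8 is one of three on-treatment samples per patient, because the Visit 5 sample precedes the first randomized dose.

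**Working it through.** **1. The four PK visits side by side**

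- Visit 5: drawn before randomized dosing; draw time recorded.
- Visit 8: window of 6 ± 2 h after dose; draw time exempted.
- Visits 12 and 14: any time after dose, on condition that dose and draw times are recorded.

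The condition on recording both times is attached to Visits 5, 12 and 14 only. The diary holds dose and meal times, not the draw. Table 7, footnote x, sets the window without asking for a time. No other section restores the Visit 8 draw time.

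**2. What is lost**

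Time since dose = draw clock time − dose clock time. With the draw time missing, an in-window sample lies between 6 − 2 = 4 h and 6 + 2 = 8 h. Used at 6 h, it is misplaced by at most 2 h.

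**3. Size on the terminal slope**

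Input: half-life 14.0 h (Table 3, healthy fed subjects, n = 5). Ratio of the true concentration to that at 6 h:

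- drawn at 4 h: 2^(2/14) = 1.104, or +10%
- drawn at 8 h: 2^(−2/14) = 0.906, or −9%

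The two ends of the window differ by 2^(−4/14) = 0.820, or 18%. That is the spread across the window, not the error against a nominal 6 h.

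**4. Sensitivity to absorption**

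This is an illustration with a one-compartment oral model. Here k = ln 2/14, and ka is solved from ln(ka/k)/(ka − k) = Tmax, using the Table 3 median Tmax of 6.0 h and its range of 2.5 to 12.0 h. At twice-daily steady state (τ = 12 h), C(t) is proportional to e^(−kt)/(1 − e^(−kτ)) − e^(−ka·t)/(1 − e^(−ka·τ)).

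| Tmax | ka (/h) | Steady state, 4 h / 8 h vs 6 h | Single dose, 4 h / 8 h vs 6 h |
|---|---|---|---|
| 2.5 h | 1.381 | +10% / −9% | +10% / −9% |
| 6.0 h | 0.396 | +4% / −7% | −5% / −3% |
| 12.0 h | 0.130 | 0% / −2% | −21% / +12% |

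The steady-state column is the relevant one. Visit 8 comes three weeks after the first randomized dose (Week 7 to Week 10), and Section 3.1.6 puts steady state at about 2 to 6 days. In this model slower absorption makes the error smaller, not larger.

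**5. Sensitivity to a faster decline**

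Table 3 gives mean AUC/Cmax = 4360/878 = 5.0 h. A one-compartment profile with a 14 h half-life would give at least 14/ln 2 = 20 h, so concentrations probably fall faster around the peak than the terminal slope implies. If 5.0 × ln 2 = 3.4 h is taken as an effective half-life, a 2 h error is about +50%/−33%. Across assumed half-lives of 6 down to 2 h, which the protocol does not give, the error runs from +26% to +100% at 4 h and from −21% to −50% at 8 h. This is rough: Cmax rests on 8 subjects and AUC on 5, and the true profile has several phases.

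**6. Could a draw fall outside the window?**

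Section 7.1 places the dose about 4 to 6 h before the visit. Vital signs (Section 10.1.2) and collection of the diary come before the blood draw, and so, when possible, do the questionnaires (Table 7, footnote m). A patient who arrives 6 h after dose has 8 − 6 = 2 h left. A late draw is possible, and without a draw time it would not be detected.

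**The case against.** **The exception is probably a misplaced qualifier.** It is followed at once by the Visit 8 window, and Section 10.1.13 then frees Visits 5, 12 and 14 from any timing. The natural contrast is fixed against free timing, and a site can hardly meet a mandatory window without noting the time. The duplicate in Section 5.8.5.1 may simply be copied text. This stands as to intent: a reader might infer a deliberate decision not to record, and the documents do not support that. It does not change what the text instructs.

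**Other documents may close the gap.** Section 9.4 refers to a Laboratory Manual and Section 11.4.4 to a separate PK analysis plan, neither of which is at hand. A laboratory form may well carry a time field, so it cannot be said that the window can never be checked. If the manual does require the time, it departs from the protocol's wording, which still needs correcting.

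**The sample is not lost.** The dose time is in the diary, Section 7.1 helps bound the interval, and Visits 12 and 14 have both times. The effect is also modest beside the 36.7% coefficient of variation for Cmax in Table 3. This stands: the loss is in precision and verifiability.

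**Visit 8 is not shown to be a near-peak sample.** That inference fits the healthy-subject median Tmax of 6.0 h. Section 3.1.6 also gives a pediatric median of 2 to 3 h, on which the window falls after the peak, and no section says that Visit 8 targets the peak. Nor is home dosing described as usual; it is only permitted.

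**Conclusion.** The text is wrong as written, at low to moderate severity. Both sections exempt from recording the draw time at the one PK visit with a required post-dose window, and nothing else in the protocol restores it. Taken literally, time since dose is unknown for one of three on-treatment samples, and compliance with the window cannot be verified from protocol-required data.

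The size is about +10%/−9% for a 2 h in-window error, assuming the 14.0 h terminal half-life applies and the sample is assigned 6 h. Slow absorption at steady state would reduce it; a faster decline around the peak would increase it. A draw outside the window would add further error without being seen.

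Three stronger readings should be resisted. The sample is not unusable, since a nominal time can be assigned. The error is not 18%, which compares the two ends of the window with each other. It is not generally larger in patients still absorbing, because that pattern appears only in the single-dose case with Tmax 12 h, and Visit 8 is at steady state. The primary HQ-CT analysis is unaffected.

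**What to change.** Delete the clause exempting Visit 8 in both Section 5.8.5.1 and Section 10.1.13. State that the actual clock time of the preceding dose and of the PK draw are recorded at every PK visit, Visit 8 included. Keep the Visit 8 window as it stands. Check that the Laboratory Manual and the sample form say the same.

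The cost is one time field on the eCRF or laboratory requisition, with no extra blood draw, visit or change to dosing. The correction should be made early, because draw times that were not recorded cannot be recovered reliably later.

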10.1.14. Food Diary

A food diary will be distributed to all patients on Visits 4, 7, 11 and 14 but can be distributed at the site's or patient's convenience. This food diary will be collected as per [Table 7](#). The food diary will collect time of food consumption, type and amount of food consumed, date and time of evening and morning dose, and support the pharmacokinetic analysis.

10.2. Adverse and Serious Adverse Events

10.2.1. Evaluation of Safety

Timely, accurate, and complete reporting and analysis of safety information from clinical studies are crucial for the protection of patients and is mandated by Regulatory Agencies worldwide. All clinical studies sponsored by Radius will be conducted in accordance with SOPs that have been established to conform to regulatory requirements worldwide to ensure appropriate reporting of safety information.

Where possible, a diagnosis rather than a list of symptoms should be recorded. All AEs should be captured on the appropriate AE pages in the electronic case report form (eCRF) and in source documents.

All AEs will be collected from the time of consent/assent until the following time points:

- For patients who are not enrolled: until time of screen failure
- For enrolled patients:
 - For patients continuing in the long-term extension study SCOUT-016: through Visit 14 (Week 34) inclusively
 - For patients entering the follow-up period with IP tapering: through Visit 16 (Week 38).

Investigators are not obligated to actively seek AEs or SAEs after the participant has concluded study participation. However, if the investigator learns of any SAE, including a death, at any time after a participant has completed the study or 30 days after the last dose of IP, and he/she considers the event to be reasonably related to the study intervention, the investigator must promptly report the SAE.

All patients will be queried using non-leading questions about the occurrences of AEs at each study visit. Adverse events spontaneously reported by the patient and/or in response to an open question from the study personnel or revealed by observation will be recorded during the study at the investigational site. When possible, a constellation of signs and/or symptoms should be identified as one overall event or diagnosis. All AEs for enrolled patients will be recorded in the eCRF and the patient's source documents. Any AEs for patients who are screened but not subsequently enrolled in the study will be recorded only in the patient's source documents. The following data should be documented for each AE by the Investigator:

- Description of the event term as diagnosis, in standard medical terminology when possible
- Classification of "serious" or "not serious"

- Date and time of the onset and resolution (if applicable)
- Severity
- Causal relationship to study drug
- Action taken with study drug
- Outcome (as applicable)
- Concomitant medication or other treatment given
- Whether or not it caused the patient to discontinue the study.

10.2.1.1 Definition of Adverse Events

An AE is any untoward medical occurrence in a clinical investigation patient administered a pharmaceutical product, which does not necessarily have a causal relationship with the treatment. An AE can therefore be any unfavorable and unintended diagnosis, symptom, sign (including an abnormal laboratory finding), syndrome or disease temporally associated with the use of a medicinal (investigational) product, whether or not related to the medicinal (investigational) product (ICH, 1995). This includes any newly occurring event which occurs during the study, having been absent at Screening, or any previous condition, if present at Screening, that appears to worsen (i.e., increased in severity or frequency) after the administration of study drug.

Study assessments including laboratory tests, ECGs, physical examinations, and vital signs should be performed and those deemed a clinically significant worsening from Screening will be documented as an AE. When possible, a clinical diagnosis for the study assessment should be provided rather than the abnormal test result alone (e.g., urinary tract infection, anemia). In the absence of a diagnosis, the abnormal study assessment itself should be listed as the AE (e.g., bacteria in urine or decreased hemoglobin).

Investigators will be requested to evaluate abnormal study assessments for clinical significance.

This would include:

- Worsening from Screening (change in nature, severity, or frequency) of conditions present at Screening
- Concomitant signs or symptoms related to the abnormal study assessment
- Intercurrent illnesses
- Drug interactions
- Events related to or possibly related to concomitant medications
- Further diagnostic testing or medical/surgical intervention is required
- Abnormal laboratory values (this includes significant shifts from Screening within the range of normal that the Investigator considers to be clinically significant)
 - An abnormal laboratory value will not be assessed as an AE unless it requires a therapeutic intervention or is considered by the Investigator to be clinically significant
- Clinically significant abnormalities in physical exam, vital signs, or weight
- A change in the dose of study drug, if study drug is withheld, or discontinuation from study drug occurs.

Hyperphagia or decreased appetite will not be considered an AE in this study unless it significantly worsens or warrants reporting in the opinion of the Investigator.

10.2.1.2 Determination of Clinical Significance Must be Made by the Investigator.

Events that do not meet the definition of an AE or SAE include:

- Planned hospital admissions or surgical procedures that are elective or for a condition that existed before the patient signed the ICF are not considered an AE unless the condition deteriorates in an unexpected manner during the study (e.g., surgery had to be performed earlier than planned)
- Anticipated day-to-day fluctuations of pre-existing disease(s), condition(s), and signs or symptoms present or detected prior to the start of the study that are not more severe than expected for the patient's condition.

